# 8.2 Agent Ordering and Agent Accountability

NCI-supplied agents may be requested by the Principal Investigator (or their authorized designee) at each participating institution. Pharmaceutical Management Branch (PMB) policy requires that agent be shipped directly to the institution where the patient is to be treated. PMB does not permit the transfer of agents between institutions (unless prior approval from PMB is obtained). The CTEP-assigned protocol number must be used for ordering all CTEP-supplied investigational agents. The responsible investigator at each participating institution must be registered with CTEP, DCTD through an annual submission of FDA Form 1572 (Statement of Investigator), Curriculum Vitae, Supplemental Investigator Data Form (IDF), and Financial Disclosure Form (FDF). If there are several participating investigators at one institution, CTEP-supplied investigational agents for the study should be ordered under the name of one lead investigator at that institution.

Active CTEP-registered investigators and investigator-designated shipping designees and ordering designees can submit agent requests through the PMB Online Agent Order Processing (OAOP) application (https://eapps-ctep.nci.nih.gov/OAOP/pages/login.jspx). Access to OAOP requires the establishment of a CTEP Identity and Access Management (IAM) account (https://eapps-ctep.nci.nih.gov/iam/) and the maintenance of an "active" account status and a "current" password. For questions about drug orders, transfers, returns, or accountability, call [contact] Monday through Friday between 8:30 am and 4:30 pm (ET) or email [contact] anytime.

# 8.2.1 Agent Inventory Records

The Investigator, or a responsible party designated by the Investigator, must maintain a careful record of the inventory and disposition of all drugs received using the NCI Drug Accountability Record Form (DARF) (available on the CTEP home page (*http://ctep.cancer.gov*) or by calling the Pharmaceutical Management Branch at [contact]). The DARFs document the drug delivery date to the site, inventory at the site, use by each study participant, and disposal of the drug (if applicable). A site-specific accountability record, either manual or electronic, may be used if it includes all the information required on the NCI Investigational Drug Accountability Record and if the paper printout is identical to the NCI accountability record. A separate DARF is required for each protocol using the same agent. The investigator will ensure that the drugs are used only in accordance with this protocol.

# 9. BIOMARKER, CORRELATIVE, AND SPECIAL STUDIES

# 9.1 Integral Laboratory or Imaging Studies

N/A

# 9.2 Investigational Device Information

N/A

9.3 Integrated Correlative Studies

N/A

9.4 Exploratory/Ancillary Correlative Studies

# 9.4.1 HTLV-1 Studies - Biological Markers of Anti-Tumor Response

# A. HTLV-1 DNA Proviral Load

Hypothesis: Nivolumab will enhance anti-ATLL immune responses and result in a decrease in HTLV-1 proviral load.

Rationale: An effective immune response against HTLV-1 should decrease the number of HTLV-1 infected cells.

Preclinical and Clinical Results: See Section 2.1 for HTLV-1 Proviral DNA and Cell-Associated and Virion RNA Load and Protein Expression (2.1.2).

Assay Methodology: Genomic DNA will be extracted from PBMCs isolated from whole blood obtained at baseline, Day 1 of Cycle 3, Day 1 of Cycle 5, every 12 weeks thereafter, and at the end of study time point, and tumor tissue at baseline and end of study time point (if available). The HTLV-1 DNA assay is performed with PBMCs, prepared in a BSL3 facility, measuring the number of copies of integrated or unintegrated viral genome with a Biorad digital drop PCR assay [53]. PCR is performed with tax primers that amplify a 154 bp region, and a FAM/MGB probe. Additionally, in a duplex PCR, a cellular housekeeping gene, ribonuclease P protein subunit P30 is amplified and detected with VIC/MGB probe. DNA will be digested with BamHI, mixed with the primers and probes and Bio-Rad 2× Supermix, and then emulsified using a QX-200 droplet generator, and PCR performed in a 96 well plate, and analyzed on the QX200 droplet reader. QuantaSoftware version 1.3.2.0 is used to quantify the copies/µl. Thresholds are determined manually for each experiment, according to the negative controls, which include a no template control and DNA from a healthy volunteer. Droplet positivity is determined by fluorescence intensity; only droplets above a minimum amplitude threshold are counted as positive. The PVL is calculated as the percentage of infected cells Data normalization is accomplished by applying the log (base 2) transformation, calculating the mean and standard deviation (SD), and defining the lower (mean-2SD) and upper (mean+2SD) values of the expected range for each assay type. These values are used to convert the log transformed values to a percentage of the expected range for each assay type, by subtracting the lower range value for the assay first then dividing by the difference of the upper and lower values of the expected range for the assay. Linear relationship of the postnormalized values is assessed using Pearson correlation.

Investigator's Experience and Competence with the Assay: [name], the Principal Investigator, used this assay in previous publications [29, 54, 55], and has funding for these studies PO1 100730, R01 CA63417, and P50 CA094056

Justification for Number of Patients and Specimens: Blood samples will be obtained at baseline, Day 1 of Cycle 3, Day 1 of Cycle 5, and every 12 weeks thereafter, and at the end of study treatment, in order to examine the correlation between proviral load, clinical response, and other correlative studies. Tumor tissue sample is obtained at baseline and off-study time point (if available) to determine proviral load in the tumor.

# **B. HTLV-1 RNA Levels**

Hypothesis: Nivolumab will enhance anti-ATLL immune responses and result in a decrease in HTLV-1 RNA levels in PBMCs and tumors.

Rationale: Nivolumab will enhance anti-ATLL immune responses and result in a more dramatic decrease in HTLV-1 RNA levels than HTLV-1 DNA levels, since not all infected cells will be expressing viral antigens.

Preclinical and Clinical Results: See Section 2.1 for HTLV-1 Proviral DNA and Cell-Associated and Virion RNA Load and Protein Expression (2.1.2).

Assay Methodology: RNA will be extracted from PBMCs isolated from whole blood obtained at baseline, Day 1 of Cycle 3, Day 1 of Cycle 5, every 12 weeks thereafter, and at the end of study, and tumor tissue at baseline and end of study time point (if available). The HTLV-1 RNA assay is performed with PBMCs. RNA extraction, complementary DNA (cDNA) synthesis, and then digital drop PCR is performed. The extracted RNA is converted to cDNA using High Capacity cDNA Reverse Transcription Kit (Applied Biosystems, Foster City, CA) according to the manufacturer's instructions. The conversion is performed using a GeneAmp 9700 thermocycler (Applied Biosystems, Grand Island, NY) with the following parameters: 10 min at 25°C, 120 min at 37°C, 5 min at 85°C, and a hold at 4°C. HTLV-1 tax and HBZ primers and FAM/MGB probes were designed for ddPCR using NCBI Primer Blast and Primer3Plus. Additionally, we amplify a housekeeping gene, Hypoxanthine-guanine phosphoribosyltransferase (HPRT), using a commercially available mix (Life Technologies, Frederick, MD). The final concentrations in the ddPCR reaction are 900 nM of each primer and 250 nM of each probe.

Digital droplet PCR is performed as described in assay methodology noted above for HTLV-1 DNA proviral load. Briefly, the cDNA is mixed with the HTLV-1 tax (or HBZ) and HPRT1 primers and probes and Bio-Rad 2x Supermix, which is then emulsified with droplet generator oil (Bio-Rad, Hercules, CA) using a QX-200 droplet generator according to the manufactuter's instructions. The droplets are transferred to a 96-well reaction plate (Eppendorf, Hauppage, NY) and heat-sealed with pierceable sealing foil sheets (Thermo Fisher Scientific, West Palm Beach, FL.). PCR amplification is performed using a GeneAmp 9700 thermocycler (Applied Biosystems, Grand Island, NY) with the following cycling parameters: 10 min at 95°C, 40 cycles consisting of a 30-s denaturation at 94°C and a 60-s extension at 59°C, followed by 10 min at 98°C and a hold at 12°C. Following PCR amplification, the 96-well plate was transferred to a QX100 droplet reader (Bio-Rad, Hercules, CA). Each well was queried for fluorescence to determine the quantity of positive events.

QuantaSoft software version # 1.7.4.0917 (Bio-Rad, Hercules, CA) is used to quantify the copies/ $\mu$ l of each queried target per well. Droplet positivity was determined by fluorescence intensity. Thresholds are determined manually for each experiment, according to negative controls, which included a no template control and cDNA from a HTLV-I seronegative healthy volunteer. All samples are run in duplicate and the gene expression is the average of the two measurements. The gene expression was normalized to the housekeeping gene expression using the following formula: Gene expression = ((quantity of HTLV-1 tax or HBZ) / (quantity of housekeeping gene))\*100.

#### **Primers and Probe Sequences:**

Gene	Forward Primer (5'-3')	Reverse Primer (5'-3')	Probe Sequence (5'-3')
Name			
Tax	ATCCCGTGGAGACTCC	CCAAACACGTAGACTGGGT	6FAM
cDNA	TCAA	ATCC	CCCCGCCGATCCCAAA
CDIWI			MGBNFQ
HBZ	AGAACGCGACTCAACC	TGACACAGGCAAGCATCG	6FAM
cDNA	GG	Α	ATGGCGGCCTCAGGGCT
UD T (IT			MGBNFQ

Investigator's Experience and Competence with the Assay: [name], the Principal Investigator, used this assay in previous publications [29, 54, 55], and has funding for these studies PO1 100730, R01 CA63417, and P50 CA094056.

Justification for Number of Patients and Specimens: Blood samples will be obtained at baseline, Day 1 of Cycle 3, Day 1 of Cycle 5, and every 12 weeks thereafter, and at the end of study treatment, in order to examine the correlation between viral RNA levels, clinical response, and other correlative studies. Tumor tissue sample is obtained at baseline and off-study time point (if available) to determine viral RNA levels in the tumor.

#### C. HTLV-1 Clonality Analysis

Hypothesis: Nivolumab will enhance anti-ATLL immune responses and result in a decrease in the clonality index of integrated HTLV-1 proviruses.

Rationale: Nivolumab will enhance anti-ATLL immune responses and result in a decrease in the clonally expanded population of infected cells, as quantified by integration site analyses.

#### Preclinical and Clinical Results: See Section 2.1 for HTLV-1 Clonality (2.1.3).

Assay Methodology: Genomic DNA will be extracted from PBMCs isolated from whole blood obtained at baseline, Day 1 of Cycle 3, Day 1 of Cycle 5, every 12 weeks thereafter, and at the end of study time point and with tumor tissue at baseline and end of study time point (if available). Clonality is determined from deep sequencing of integration sites [56]. Ten micrograms of DNA from uncultured PBMCs or tumor cells is sheared by sonication. DNA ends are then end-repaired using T4 DNA polymerase, DNA polymerase I Klenow fragment, T4 polynucleotide kinase. Addition of an adenosine at the 3' ends of the DNA is performed with Klenow Fragment 3' to 5' exo. One hundred pmol of a partially double stranded DNA linker is ligated to the DNA ends. Twenty six different linkers are constructed, each one with a specific 6bp tag to allow multiplexing of DNA samples during the sequencing. The ligated product is then split into 3 aliquots and each aliquot used in a separate PCR reaction. For each PCR reaction, ligated product is 50 pmol of B3 primer (binds HTLV-1 LTR), 10 pmol of B4 primer (which anneals to the strand of the linker generated by the amplification from Bio3), Phusion DNA polymerase. The 3 PCR1 products, derived from the same sample are then pooled, and PCR2 performed with PCR1 product using 25pmol of P5B5 primer (binds HTLV-1 LTR), 25 pmol of P7 primer (binds the linker), Phusion DNA polymerase. A library is constructed by pooling the different PCR2 products (each one possessing a specific tag). Quantification of the libraries is made by OPCR using primers P5 and P7 libraries are diluted to 0.5 pM and clustered on the Illumina flow cell. Paired-end reads (read1 and read2 each 50bp) plus a 6 bp tag read (read 3) are acquired on a GA II. The library construction pipeline is split into four steps: 1. DNA isolation and shearing; 2. Pre-PCR manipulations (ends repair and ligation); 3. PCR1 and PCR2 and library QPCR; 4. Library sequencing. Each step is carried out in a specific room and the sample flow is unidirectional, to minimize the risk of PCR contamination.

Read 1 and read 2 are mapped against the HTLV-1 and the human genome. First, overlapping clusters are exclude and then the following quality control filters: i) the single-read alignment scores of read 1 and read 2 must be higher than 10, ii) the strand orientation of the 2 reads must be opposite; iii) the length of the amplicons must be smaller than 1kb. Because the PCR is not specific to the 3'LTR, we discard the amplicons generated from the 5'LTR that contained only HTLV-1 sequences. We identify read 1 sequences that start with ACACA (the five bases at the 3' terminus of the HTLV-1 LTR). Read 1 and read 2 sequences are used to map the insertion site and the shear site. Read 3 is used to allocate the insertion site to a particular sample. Together with the mapping of a large number of UISs, the goal of our approach is to quantify the abundance of each unique integration site (UIS). Because PCR preferentially amplifies short products, the number of amplicons cannot be used to quantify the abundance of a given UIS. Random DNA fragmentation by sonication is a key feature to allow the quantification of the UIS abundance because, it is not biased to particular nucleotide sequences. For each UIS, we count the number of amplicons of different length. Additionally, misreading of the tag index during the sequencing could lead to the attribution of a particular insertion site to different samples. We solve this issue by taking into account not only the 6bp tag information but also the total number of distinct shear sites and the total number of reads

for a given insertion site to attribute the insertion site to the correct sample. Finally, control DNA (from a human T-cell line (Jurkat) uninfected by HTLV-1) is run on every lane of each flow cell to assess the effectiveness of our quality control procedures. Clonality is then determined from the oligoclonality index.

Investigator's Experience and Competence with the Assay: [name], the Principal Investigator, used this assay in a previous report [55], and has funding for these studies PO1 100730, R01 CA63417, and P50 CA094056.

Justification for Number of Patients and Specimens: Blood samples will be obtained at baseline, Day 1 of Cycle 3, Day 1 of Cycle 5, and every 12 weeks thereafter, and at the end of study treatment, in order to examine the correlation between clonality, clinical response, and other correlative studies. Tumor tissue samples are obtained at baseline and off-study time point (if available) to determine clonality in the tumor.

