#### **1.2** Secondary Objectives

- 1. To determine effects of nivolumab on HTLV-1 proviral DNA and RNA loads.
- 2. To determine the effects of nivolumab on anti-HTLV-1 and anti-ATLL immune responses.
- 3. To determine effects of nivolumab on HTLV-1 integration site clonality.

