# 2.1.3 HTLV-1 Clonality

In ATLL, there is a clonal expansion of T cells with clonal T-cell receptor gene rearrangements

and clonal sites of provirus integration into chromosomal DNA, as determined by Southern blot hybridization [12]. More recently, a ligation mediated PCR technique has been utilized as a more sensitive way to detect different clonal populations in asymptomatic infected individuals, HAM patients, and ATLL patients [13]. These studies have demonstrated that the expanded clone of malignant ATLL has arisen from an oligoclonal expansion of HTLV-1 infected cells. These studies suggest that HTLV-1 dissemination can occur by viral replication and clonal expansion of infected cells.

A recent study examined the genomic characteristics of the integration sites in 197 ATL cases [14]. In 91% of cases, a single predominant provirus was present; in 11% of the total 2 proviruses were present in a single tumor clone. In 9% of cases, no significant difference in the abundance of two integration sites was seen. A complete provirus was present in 46% of cases, 39% of cases contained a defective provirus, 7% contained a nonsense mutation of the *tax* gene, and 8% contained a hypermethylated promoter in the 5'LTR. The host genomic characteristics of the integration site in the large ATL clones closely resembled those of low-abundance clones present in subjects with nonmalignant HTLV-1 infection. These authors concluded that the major determinant of the risk of ATL is the absolute number of clones, i.e. the larger the number, the greater the chance of malignant transformation. They also suggested that the number of HTLV-1 infected clones present in an individual during chronic infection is determined chiefly by the efficiency of the host's CTL response to the virus.

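### The clonality assay sizes each clone by a count that cannot exceed 999 and has no written correction, so a large fall in a heavily sampled dominant clone can be understated

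*Combined protocol and SAP*

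**What the plan says.** Section 1.2 lists as its third secondary objective: "To determine effects of nivolumab on HTLV-1 integration site clonality". Section 9.4.1 C states the hypothesis that treatment will "result in a decrease in the clonality index of integrated HTLV-1 proviruses".

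The assay methodology in the same section starts from a fixed mass of DNA: "Ten micrograms of DNA from uncultured PBMCs or tumor cells is sheared by sonication". A quality filter requires that "the length of the amplicons must be smaller than 1kb". Read counts are ruled out as a measure of clone size: "Because PCR preferentially amplifies short products, the number of amplicons cannot be used to quantify the abundance of a given UIS". The measure used instead is "For each UIS, we count the number of amplicons of different length". The final step is "Clonality is then determined from the oligoclonality index", and no formula for that index is given.

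The section describes no correction for cells of one clone that shear at the same length, no calibration or dilution step, and no flag for a site near the maximum count. For the method it refers to a cited source (reference 56).

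**The concern.** Counting distinct shear lengths is a sound way round PCR bias while a clone contributes few fragments, because two fragments then seldom share a length. As fragments accumulate, more of them repeat a length already seen, and the count flattens toward the number of lengths available. A large clone is therefore compressed far more than a small one.

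ATLL is a disease in which one clone usually stands out. Section 2.1.3 reports from a series of 197 cases: "In 91% of cases, a single predominant provirus was present". The planned comparison is before against after treatment. If the dominant clone lies on the flat part of the curve at baseline, killing most of it moves the count little, and its share of infected cells is misstated at both visits. The degree of compression also depends on how many molecules are recovered, so two samples with different recovery are not on the same scale.

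**Working it through.** The documents give no numerical clonality figure to reproduce. What can be checked is how the stated rule behaves.

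**Inputs from Section 9.4.1 C.** Abundance is the number of distinct lengths per site; lengths are below 1 kb; input is 10 micrograms of DNA.

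**Assumed, because not stated.** 6.6 pg of DNA per diploid cell; dominant clone in 50% of PBMC; a further 5% of PBMC in 2,000 small clones, left unchanged; usable lengths 40 to 999 bp; shear lengths either log-normal (mean 300, SD 150 bp) or uniform; recovery between 0.01% and 10% of molecules.

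**Ceiling.** Whole-number lengths below 1,000 allow at most 999 values. Input genomes = 10 µg / 6.6 pg = about 1.515 million.

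**Expected count.** With n recovered fragments of a clone and p_l the probability of length l,

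D(n) = sum over l of [1 − exp(−n p_l)].

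For the assumed clone, n = 1.515 million × 0.5 × recovery before treatment, and one tenth of that after a true tenfold kill. The counted fall is D(n) / D(n/10).

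| Recovery | n before / after | Distinct lengths, log-normal | Counted fall, log-normal | Counted fall, uniform |
|---|---|---|---|---|
| 0.01% | 76 / 7.6 | 69 / 7.5 | 9.3 | 9.7 |
| 0.1% | 758 / 76 | 378 / 69 | 5.5 | 7.2 |
| 0.5% | 3,788 / 379 | 630 / 256 | 2.5 | 3.0 |
| 1% | 7,576 / 758 | 723 / 378 | 1.9 | 1.8 |
| 10% | 75,758 / 7,576 | 938 / 723 | 1.3 | 1.0 |

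**Threshold.** Over four shear profiles (uniform, log-normal, exponential, normal) on lengths 50 to 999 bp, the counted fall drops below twofold once n reaches about 5,800 to 8,000. Against 1.515 million genomes, 6,000 is 0.40% and 8,000 is 0.53%.

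**Dominant clone's share of infected cells at 1% recovery.** The true share goes from 50/55 = 91% to 5/10 = 50%. The small clones yield about 758 molecules, counted as about 742 lengths if their sizes fall off as 1/rank. The counted share is then 723/(723 + 742) = 49% before and 378/(378 + 742) = 34% after. With equal-sized small clones it is 49% to 33%.

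**Index.** No formula is given, so a Gini coefficient was taken as an assumption, computed only on sites that yield at least one fragment.

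- Small clones as 1/rank, 1% recovery: 0.745 to 0.669, against a true 0.977 to 0.877. About three quarters of the true fall is seen (0.076 of 0.100).
- Same clones, 0.1% recovery: about 0.86 to 0.60. The observed fall of 0.26 exceeds the true 0.10, because many small clones are not seen at all.
- Equal-sized small clones, 1% recovery: about one third of the true fall is seen.
- Either pattern, 10% recovery: less than a tenth is seen.

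**Does inverting the count work?** Solving D(n) = k with the log-normal profile takes 723 and 378 back to about 7,600 and 760, a tenfold ratio. In simulation with that profile known, the 95% range of estimates was about 6,500 to 8,700 for a true 7,576, and 17,500 to 23,300 for a true 20,000. Under uniform lengths with 950 values, counts of 910 and 257 return 3,000 and 300, but at n = 10,000 the expected count is already 950 of 950 and inversion fails.

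**The case against.** The strongest reply is that the documents do not show that this assay reaches the flat part of the curve. Recovery, read depth, shear profile and clone share in blood are all absent. At 0.1% recovery a tenfold fall still appears as 5- to 7-fold. The 91% figure says that one provirus predominates, not that it fills the blood. Section 3.1 admits every subtype, and Section 2.1.1 describes smoldering disease as having little blood involvement, so some patients may never approach the ceiling. This stands: the compression is conditional.

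A reader might go further and infer that a dominant ATLL clone necessarily saturates, that the clonality index will barely move, or that the error always runs toward no effect. The documents support none of these. The index has no formula, and under an assumed Gini the observed fall ranges from less than a tenth of the true fall to more than twice it, depending on recovery and on small-clone sizes that are not given.

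It can also be said that the cited method source may contain a correction. That cannot be judged here, and the plan's own steps do not include one. Finally, the assay sits under exploratory studies in Section 9.4, Section 13.3 makes the analysis descriptive, and droplet-PCR proviral load (Section 9.4.1 A) would show a large fall in infected cells without this ceiling. That limits the damage, but proviral load cannot show which clone fell, which is what objective 3 asks.

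**Conclusion.** The point holds in conditional form. As written, the abundance measure has a hard ceiling of 999 and no correction for repeated lengths. If about 6,000 to 8,000 or more fragments of a dominant clone are recovered, a true tenfold fall is counted as less than twofold. In that range the clone's share is also distorted (49% to 34% counted against 91% to 50% true in the 1% example). At 0.01% recovery the bias is small. These sizes rest on the assumed DNA mass per cell, clone share, shear profiles and recovery. The consequence for the oligoclonality index cannot be sized or signed until the index is defined. Only secondary objective 3 is affected; the primary endpoints are not.

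**What to change.** Add to the assay methodology in Section 9.4.1 C, before the index is computed:

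1. Convert each site's distinct-length count k to an estimated number n of sister cells sampled (recovered fragments) by solving k = sum over l of [1 − exp(−n p_l)], with p_l taken from the run's own fragment-length distribution.
2. Give the formula of the oligoclonality index, and compute both it and the dominant clone's share from n.
3. Report sites at or near the ceiling as lower bounds, with the uncertainty of n for large clones.

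The cost is one analysis step on data the assay already produces. For very large clones the estimate will be imprecise. Where lengths are near uniform and the count is fully saturated, only a lower bound will be available.
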